- After screening, consent forms, signed by the person who will be obtaining consent, are mailed to the participant with a post-paid return envelope. Written informed consent from the participant is an integral part of the study. Informed consent will follow the procedures of the IRB and Research and Development (R&D) Committee of the VAMC Memphis. All participants **must** give written informed consent before becoming study participants and assent must be obtained from the service member and reported by the participant.
- During the informed consent call the potential participant will be asked to read the informed consent and be given the opportunity to ask questions. A Research Associate will review all key aspects of the study with the potential participant. Staff will question to ascertain whether the potential participant has understood the information. Potential participants who are illiterate or have impaired vision will have the consent read to them and will be given an opportunity for questions and discussion. A signed informed consent is required prior to data collection. Participants will be encouraged to ask for clarification about the forms and discuss concerns about the study at this time.
- The consent form is carbon color coded. After the participant initials and signs the form, one copy of each page is kept by the participant, and one is filed in the study office. To protect participant confidentiality and per IRB waiver, no witness is required.
- After consent is obtained and baseline data collection, the Data Analyst (DA) will randomly assign each participant to one of the study arms. Participants are independently assigned to study arms and there will be no stratification based on covariates at the time of assignment to study arm. The DA will maintain a confidential, locked register of names, study identification numbers, and treatment arm assignments.

- As soon as baseline data collection and randomization are completed for a participant, a staff member will call and provide information on assignment and the intervention.

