The values tabulated in the Detectable Difference column of the table document the minimum true between contrast group difference in gain scores in population data sampled needed for statistical power to attain 0.80 or better to reject a false null hypothesis of no group by time interaction effect in repeated measures data. In general terms, we will have statistical power of 0.80 or better to reject a false null hypothesis when the between contrast group difference in gain scores attains approximately 0.30 or more of the population standard deviation estimated from REACH and READI study baseline data. For statistically significant comparisons, effect size of  $d \geq 0.2$  will be considered clinically significant, consistent with psychosocial interventions' small to medium effect sizes (46). Interaction effect sizes will be estimated as mean between-group gain score change relative to estimated population standard deviation (106).

**Mixed-Effects Modeling Approach.** Randomization into the two arms, respectively, guarantees that individuals are not systematically assigned to one arm. Regardless, when analyzing the data it should be beneficial to account for the actually present covariates for the individuals. In addition, the mixed-effects modeling approach allows us to incorporate individuals in the study who are lacking the final outcome measurements after six months. Furthermore, we can utilize all the information from the data and can utilize the post-intervention measurements for the individuals.

We will fit separate mixed-effects models for each of the primary outcomes. For each of the  $i = 1, \dots, 160$  individuals there are  $n_i$  measurements available (for a specific outcome). The primary outcomes are measured at baseline (B), and after three, and six months ( $t = B, 3, 6$ ). It is not essential that the measurements are taken for all individuals at the same time, but we do not elaborate on this here because the data collection is planned to follow the above timeline. If all measurements are available for an individual,  $n_i = 3$  (for each primary outcome). Each individual will have measurements for at least baseline, so  $n_i \geq 1$  for all  $i$ . In mixed-effects models "individuals borrow strength" from each other and it is therefore not required that all individuals have two or more measurements in order to fit straight lines to each individual.

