We build the mixed-effects models by a forward selection procedure for the covariates of particular interest to us. Because over-parameterization is a concern in this analysis, we will give priority to covariates that are individually contributing to the model fit (evaluated by significance of parameters in the model as well as AIC and SC) and are (if possible) independent of each other. To improve model fitting we will center or standardize some or all covariates. Interaction terms will be included as needed.

We investigate intervention effectiveness by comparing the slope of the linear fits for individuals that were assigned to individual sessions with the slope of individuals that were assigned to the webinars. A mixed-effects model contains *fixed effects* and *random effects*. The mixed-effects model allows us to study whether other variables are an important factor for the development of the primary outcomes. Besides the indicator of individual  $i$  intervention assignment and demographic information such as race, age, or rural/urban location, covariates of interest to us are the participant's family composition, participant gender, and the general social support the caregiver receives. We also collect the participant's perception of the patient's disability at baseline (WHODAS 2.0 level of disability from 0 to 100) and will investigate the role that covariate might play in each model. These questions will be addressed by investigating the statistical significance of the corresponding parameters in the fitted mixed-effects model. SPSS will be used for analysis.

In addition, we will investigate possible drop out patterns in the data. This is, however, an exploratory part of our analysis and we will assume that measurements are *missing at random* in the primary analysis.

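### The mixed model tests Hypothesis 2 on the between-arm slope, but forward selection with no named covariate-by-time terms secures no precision for that contrast and leaves the model to the data

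*Combined protocol and SAP*

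**What the plan says.** All references are to the Combined protocol and SAP.

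- **Assignment** (Participant Identification and Recruitment, under telephone screening and consent): "there will be no stratification based on covariates at the time of assignment to study arm". Any control of chance differences between arms is therefore left to the analysis.
- **Reason for covariates** (Sample Size and Statistical Power, Mixed-Effects Modeling Approach): after noting that randomization prevents systematic assignment, the plan adds that "when analyzing the data it should be beneficial to account for the actually present covariates for the individuals".
- **Test of Hypothesis 2** (same place): effectiveness is judged by "comparing the slope of the linear fits for individuals that were assigned to individual sessions with the slope of individuals" assigned to the webinars, with outcomes at baseline, 3 and 6 months.
- **Model building** (same place): forward selection, in which "we will give priority to covariates that are individually contributing to the model fit". The yardsticks are parameter significance, AIC and SC. Over-parameterization is named as a worry. On interactions the text says only "Interaction terms will be included as needed".
- **Other purposes** (same place): to learn "whether other variables are an important factor for the development of the primary outcomes". The Hypotheses section says confounders will be controlled for, and explains this as asking whether impact is the same across participants who differ on them.

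Nowhere is a covariate-by-time term named, and nothing says when an interaction counts as needed.

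**The concern.** The quantity tested is a difference in change over time. A fixed baseline characteristic, such as caregiver age or the patient's WHODAS 2.0 score, improves the precision of that quantity only through its relation to change, which is a covariate-by-time term. The plan neither commits to such terms nor fixes the list of covariates.

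Two things follow. An analyst can comply fully, report a covariate-adjusted result for Hypothesis 2, and have an estimate that is practically the unadjusted one. A second analyst, equally compliant, can add time interactions and obtain a different estimate. Significance and information criteria then decide, after the data are in, which result is reported. At stake are some precision and the pre-specification of the main comparison.

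**Working it through.** **1. The plan's own figures.** Inputs from Table 2: PHQ-9 SD 5.94, r 0.84, difference 1.78; GAD-7 5.14, 0.83, 1.54; Zarit 9.74, 0.88, 2.92; two-sided 0.05; 60 completers per arm.

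SD of gain = SD × √(2(1 − r)), which gives 3.360, 2.997 and 4.772. Power at the tabled differences is 0.827, 0.804 and 0.918, so the stated 0.80 or better is reproduced. With 80 × 0.8 = 64 per arm it is 0.850, 0.828 and 0.933. These figures use unadjusted gain scores and do not depend on this point.

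**2. Why a main effect drops out.** With visits at 0, 3 and 6 months the least-squares slope is (3·y6 − 3·y0)/18 = (y6 − y0)/6. A baseline covariate c with main effect γ adds γc to every visit: (y6 + γc − y0 − γc)/6 = (y6 − y0)/6. With complete data the arm difference in slope is therefore the same with or without c.

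**3. Simulation check.** REML mixed models, PHQ-9 inputs, 80 per arm, true slope difference −1.78/6 = −0.297 points per month. Assumptions not in the documents: covariate–outcome correlation 0.5; covariate effect on slope 0 or 0.3 points per month per SD; random-slope SD 0.25; dropout dependent on the covariate.

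| Model compared with no covariate | Data | Change in arm-by-time estimate | SE ratio |
|---|---|---|---|
| Main effect only | Complete | at most 2e-14 | 1.000 (random intercept); 0.977–1.000 (with random slope) |
| Main effect only | About 19% dropout | 0.05–0.08 SE on average; largest 0.018–0.041 points/month | 0.965–1.008 |
| Plus covariate-by-time, covariate predicts slope | Both | 0.36–0.44 SE on average | mean 0.90–0.94 |
| Plus covariate-by-time, covariate does not predict slope | Both | 0.05–0.09 SE on average | mean 1.001–1.003 |

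Hand check of the unadjusted SE: 3.360 × √(2/80)/6 = 0.0885; simulated, 0.0882. Hand check of the gain with a random slope and complete data: the variance of change due to the covariate is (0.3 × 6)² = 3.24, out of 2 × 0.16 × 5.94² + (0.25 × 6)² + 3.24 = 11.29 + 2.25 + 3.24 = 16.78. That is a share of 0.193, and √(1 − 0.193) = 0.898; simulated, 0.896.

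**4. Size of the gain.** With R² the assumed share of change variance explained, the SE is multiplied by about √(1 − R²). PHQ-9, 64 per arm, difference 1.78:

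| R² | SE of gain difference | Reduction | Power |
|---|---|---|---|
| 0 | 3.360 × √(2/64) = 0.594 | – | 0.850 |
| 0.02 | 0.588 | 1.0% | 0.857 |
| 0.05 | 0.579 | 2.5% | 0.867 |
| 0.10 | 0.564 | 5.1% | 0.885 |
| 0.20 | 0.531 | 10.6% | 0.918 |

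Simulated trials with attrition gave roughly 2 to 13% over R² of 5 to 20%.

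**5. What screening would admit.** Assumed covariate unrelated to baseline and explaining 10 to 20% of change variance; 80 per arm; 20% missing at month 6; compound-symmetric covariance taken as known; 3,000 trials. Screened as a main effect, it was admitted at p < 0.05 in 20–39% of trials and by AIC in 39–61%. Tested as covariate-by-time, it was detected in 97–100%.

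**The case against.** The strongest reply is that the plan does not specify the model that loses the precision. Several stronger readings are tempting, and the documents do not support them.

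- *A reader might infer that covariates are chosen for their fit to the outcome level.* The text says model fit. A covariate-by-time term could be chosen on the same criteria, and interactions are expressly allowed. Screening as main effects is the usual first step in forward selection, but it is an inference.
- *A reader might infer that a main effect cannot change the contrast.* That is exact only with complete data. The plan allows 20% attrition and keeps incomplete cases, and the estimate then moves slightly.
- *A reader might infer that a promised benefit is not delivered.* The benefit sentence is general and promises no sharper slope contrast. Learning which factors relate to outcomes is a stated purpose that main effects can serve. The Hypotheses section does speak of control, but explains it as equivalence of impact, which is a covariate-by-arm-by-time question.
- *A reader might infer that chance imbalance biases the unadjusted result.* It does not. The typical imbalance, √(2/80) = 0.16 SD, is already part of the standard error under randomization.

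All four replies stand. They do not close the gap: permission to add interactions as needed is not a specification, and the worry about over-parameterization in the same paragraph pulls against adding them.

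**Conclusion.** The point holds as one of under-specification and forgone precision. The plan tests a slope contrast but fixes neither which covariates enter nor whether any enters with time. Main effects alone would do little or nothing for that contrast, and screening covariates as main effects would often miss those that matter for change.

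The unadjusted comparison is valid and the sample size stands. The size of the gain rests on an assumption: at 5 to 20% of change variance explained, the standard error falls by about 2 to 13%, and PHQ-9 power at 1.78 points with 64 per arm rises from 0.85 to 0.87–0.92. Below about 2% explained there is essentially no gain. The protection from data-driven model choice does not depend on that assumption.

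**What to change.** In the Mixed-Effects Modeling Approach text, replace forward selection for the Hypothesis 2 model with a short list of baseline covariates fixed before unmasking, for example WHODAS 2.0, social support and caregiver age. Enter each, centered as the plan already foresees, with its main effect and its covariate-by-time term, not crossed with arm. Do so in all three outcome models whatever the significance, and read Hypothesis 2 from arm-by-time. Because no added term involves arm, that coefficient keeps its meaning. Keep forward selection and covariate-by-arm-by-time terms as labeled exploratory analyses; they serve the equivalence-of-impact question.

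Cost: a change of wording, since the variables are already collected at baseline. Each covariate uses two parameters, so three use 3 × 2 = 6 with 160 participants. If a covariate does not predict change, the simulated loss is an SE increase of 0.1 to 0.3%.

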## **Data Analysis**

Primary outcomes are measured for all participants at baseline, at three months, and after six months. We estimate the necessary sample size based on analysis of a pretest-posttest control group design. The final analysis of the data will, in addition to this approach, use a mixed-effects model. These models allow us to assess whether other factors, such as a participant's age or the patient's level of disability, are related to the measured outcomes.

Randomization will likely lead to slightly different group sizes in the study arms because participants are independently assigned to the arms, but we are not concerned about this as group sizes will also be different due to expected drop outs in each group. Once assigned to a study arm, participants will be considered in the study and we will primarily follow an intention-to-treat (ITT) approach, both for ANOVA and the mixed-effects modeling approach described below. Individuals will be included in their assigned group even if they do not participate in some or all of the intervention components (i.e., does not comply with the “treatment”).

The benefit of ITT is twofold. First, we do not bias the result by defining “sufficient compliance” with the treatment/intervention after data are collected. Second, we assure that our study result is relevant in the sense that any effect of the intervention is actually achievable with the level of encouragement to stay in the intervention as provided in this study. Especially, potential future benefits from the intervention will *not* be conditional on future participants who comply fully with the advised meetings and exercises, even in case many individuals have difficulties in study compliance.

Having said that, we will record the level of participation for each individual in each intervention arm (number of sessions that the individual participated in), and we will investigate the importance of this compliance. We expect that compliance will be an important indicator of how engaged an individual was, and how much of the offered support or education an individual could benefit from. This is an exploratory part of our data analysis.

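### Covariates are picked on significance and then judged important on significance in the same fitted model, with no multiplicity control and no exploratory label

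*Combined protocol and SAP*

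**What the plan says.** The relevant text is the Mixed-Effects Modeling Approach, under Sample Size and Statistical Power, with its rationale in Data Analysis.

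- Purpose. Data Analysis says of the mixed models and the trial's outcomes: "These models allow us to assess whether other factors, such as a participant's age or the patient's level of disability, are related to the measured" (last word omitted). The modelling section repeats the aim: "The mixed-effects model allows us to study whether other variables are an important factor for the development of the primary outcomes".
- Model building. "We build the mixed-effects models by a forward selection procedure for the covariates of particular interest to us". On the criterion, "we will give priority to covariates that are individually contributing to the model fit", and this is "evaluated by significance of parameters in the model as well as AIC and SC". No entry threshold is given, and interactions may be added at the analyst's discretion.
- Candidates. The section names "demographic information such as race, age, or rural/urban location", then family composition, participant gender, social support and baseline WHODAS 2.0 disability. That makes seven, and the demographic list is given only as examples. The Hypotheses section adds sessions completed, care provided and type of injury.
- Inference. "These questions will be addressed by investigating the statistical significance of the corresponding parameters in the fitted mixed-effects model".
- Scope. A separate model is fitted for each of depression, anxiety and burden.

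The plan attaches an exploratory label to the compliance analysis (Data Analysis) and to drop-out patterns (end of the modelling section). It attaches none to the covariate questions, and it gives no multiplicity rule for them.

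**The concern.** The same data and the same statistic are used twice: once to let a covariate into the model and once to decide whether it matters. An ordinary p-value assumes that the covariate was fixed in advance. Here it is a covariate kept because its estimate happened to be large in these data, so its final p-value and interval do not have their usual meaning.

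Separately, at least seven covariates are judged in each of three models with no adjustment, so some false finding is likely somewhere even if every individual test is sound.

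At stake are the plan's statements about which caregiver or patient characteristics are related to depression, anxiety and burden. A reader could take a chance finding for an established predictor, or take an overstated coefficient at face value.

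**Working it through.** The documents state no error rate for the covariate tests, so there is no figure of the plan's own to reproduce.

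**Inputs from the documents.** 160 participants, 80 per arm; three outcomes; seven named covariates; two-sided 0.05 (stated for the power calculation and assumed here for the covariate tests, since no other level is given).

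**Assumptions.** Each covariate takes one parameter and has no effect; outcomes correlate 0.6 (varied from 0 to 0.8); covariates are independent (also run at correlation 0.3). The main simulation is a subject-level regression with arm always included, 1,000 replicates per rule.

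**Step 1: what each entry rule implies for one null covariate.** The likelihood-ratio gain is approximately chi-square with 1 df.

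- Significance: gain above 1.96² = 3.84, tail 0.05.
- SC: gain above ln(160) = 5.08, tail 0.024. This is stricter than 0.05, so an entrant is already significant.
- AIC: gain above 2, tail 0.157. The share of entrants also below 0.05 is about 0.05/0.157 = 32%.

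**Step 2: at least one false factor, no selection, one outcome.** 1 − 0.95^7 = 30.2%.

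**Step 3: simulated forward selection, seven null covariates.**

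| Rule | False-positive rate per covariate | Null covariates entering | Entrants significant in final model | Any false factor, one outcome | Any false factor, three outcomes |
|---|---|---|---|---|---|
| p<0.05 | 5.1% | 5.1% | 100% | 30% | 58% |
| p<0.05 or AIC | 5.8% | 17.1% | 34% | 34% | 63% |
| p<0.05, AIC and SC jointly | 2.7% | 2.7% | 100% | 17% | 38% |
| Fixed model, all seven, unadjusted | 5.0% | n/a | n/a | 30% | 58% |

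**Step 4: sensitivity.**

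- Outcome correlation 0.8 to 0, p<0.05 entry: 53% to 66% over three outcomes.
- Covariate correlation 0.3, seven candidates: 2.3% to 6.3% per covariate, 15% to 35% per outcome.
- Fourteen independent candidates (for example, each covariate plus its time interaction): 33% to 55% per outcome, 64% to 85% over three outcomes.
- Fourteen candidates with covariate correlation 0.3: up to 7.1% per covariate.
- A random-intercept mixed model (160 people, three visits, 20% missing at month 6, intraclass correlation 0.84, p<0.05 entry, 223 replicates): 36% per outcome (Monte Carlo SE 3 points), 6.0% per covariate, and 94 of 94 selected null covariates significant.

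**Step 5: overstatement of real effects.** Take an assumed true effect of 0.15 SD per SD of covariate. The mean estimate when selected was 0.21 to 0.22 (p entry), 0.19 to 0.20 (AIC), 0.23 (SC) and 0.24 (joint). A fixed full model gave about 0.15. After selection, interval coverage for this effect was 91% to 95%. For null covariates that entered on p, SC or the joint rule, the 95% interval covered zero 0% of the time.

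**Step 6: effect of adjustment.** With a fixed model and a first Holm threshold of 0.05/7, any false factor per outcome is 1 − (1 − 0.05/7)^7 = 4.9%. Over three independent outcomes, each held at 5%, it could reach 1 − 0.95³ = 14%. Across all 21 tests it is 1 − (1 − 0.05/21)^21 = 4.9%.

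**The case against.** A reader might infer that covariates with no effect will routinely be reported as important. The documents do not support that. The error rate for any one named covariate stays at about 2% to 7%, close to nominal. What is common is at least one false factor somewhere.

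A reader might also blame the forward selection for that overall rate. The fixed model without adjustment gives almost the same 30% and 58%, so the main driver is many unadjusted tests. Selection does its own, different harm: overstated estimates and uninterpretable p-values for whatever is kept.

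Nor does the text say that meeting any one of the three criteria is enough. Its wording can be read as requiring them jointly, which gives the lower figures (17% and 38%). It speaks of priority rather than exclusion, and it means to examine WHODAS in every model, so selection is not strictly a gate. These points lower the rates. They do not validate the inference: under the joint rule every null entrant is still significant, and the overstatement is the largest of the rules tried.

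It is fair that comparing 100% with 5% sets a conditional rate against an unconditional one and is close to true by definition, and that a very small final p-value still says more than one of 0.04. It is also fair that no stated hypothesis or technical aim concerns predictors, that covariates appear under Hypotheses as confounders to control, that mixed models are also justified by incomplete follow-up, and that the planned dissemination is chiefly of manuals and materials. These points limit the importance of the concern to secondary conclusions. Finally, the simulation is mostly a subject-level proxy, though the mixed-model check agrees with it.

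**Conclusion.** The concern holds for the covariate conclusions only. The plan states a rule that selects on significance and then infers from significance in the same model, across an open list and three outcomes, with neither adjustment nor an exploratory label. That makes it a defective rule rather than missing detail.

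The size depends on how the entry criteria are read and on the number of candidates. The main figures (17% to 34% of models, 38% to 63% of trials) rest on seven independent single-parameter candidates, a 0.05 level and outcome correlation 0.6. Race or family composition with several categories would change the counts, and added interactions would raise the rates. The overstatement of a 0.15 SD effect rests on that assumed value; for that effect the intervals remained close to nominal, so a general claim that intervals fail after selection would go too far.

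The arm-by-time comparison was not tested here, and nothing in this point bears on it.

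**What to change.** For the covariate questions, replace forward selection with one fixed model per outcome containing arm, time, arm-by-time and the seven covariates already named in the modelling section, at their baseline values. Report every coefficient with its 95% CI, significant or not. Call a covariate important only after Holm adjustment across the named covariates within each outcome (about 4% to 5% chance of any false factor per outcome). Apply Holm across all three outcomes if the trial-wide rate, otherwise up to about 14%, is to be held at 5%.

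State whether the question concerns level or change over time. If change, apply the same rule to prespecified covariate-by-time terms. Report any further covariate or interaction found by selection as hypothesis-generating only, and amend the inference sentence to refer to the fixed model.

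The cost is wording, with no new data or participants. There are two downsides. More parameters are estimated from 160 people: 160/7 is about 23 participants per covariate term, falling to 160/14, about 11, with a time interaction for each, and lower still if race or family composition has several categories. The plan's own worry about over-parameterization is therefore relevant to the second version. Holm will also leave fewer covariates declared significant.
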